## 1.0 PROTOCOL SUMMARY AND/OR SCHEMA

### Protocol Summary

This is a phase II, single-arm trial assessing local control (ie. no local failure) after near-total endoscopic resection (NTR) followed by concurrent chemotherapy with proton-beam radiation in unresectable tumors (which we define as expected inability to perform negative margin surgery) of the paranasal sinuses and nasal cavity. We will compare rate of local failure at 1 year after treatment in those undergoing NTR and adjuvant treatment with historical rates of failure in those undergoing non surgical management. As secondary and exploratory endpoints, we will assess other oncologic outcomes (overall survival, progression free survival, etc), physician reported complications of surgery and chemoradiation toxicity, and patient reported outcomes, and will store tissues obtained for IMPACT testing.

We plan to have 25 eligible patients, 15 of which will be Squamous Cell Carcinoma patients and the rest 10 shall be Adenoid Cystic Carcinoma, Esthesioneuroblastoma, or Adenocarcinoma patients.

### Protocol Schema

## 2.1 OBJECTIVES AND SCIENTIFIC AIMS

## **Primary Objective**

- To determine if near-total resection with minimally invasive endoscopic approach for unresectable paranasal sinus / nasal cavity tumors followed by concurrent chemotherapy and proton-beam radiation improves local control at 1 year after treatment compared to traditional approaches of nonsurgical management alone. Our historical data showed that the rate of local failure at 1 year with chemotherapy and IMRT alone is 50%. We hypothesize that adding NTR and proton radiation with chemotherapy will reduce the rate of local failure at 1-year to 25%. Local failure will be defined using a modification of RECIST 1.1.

## **Secondary Objectives**

- To assess the complications of treatment related to minimally invasive endoscopic skull base surgery in patients with unresectable disease using Clavien-Dindo classification of surgical complications
- To assess toxicity of treatment based on CTCAE v4.03 scores in the acute setting (throughout treatment and up to the 3 month visit after end of treatment)
- To assess toxicity of treatment based on CTCAE v4.03 scores in the long-term setting (after the 3 month post treatment visit until the 24 month post treatment visit)
- To assess toxicity of treatment related to patient reported outcomes including EORTC (H&N43 and C30) and Skull Base Inventory (SBI)
- To determine the 1- and 2-year rates of regional/nodal, or distant-metastasis progression incidence, progression-free survival, disease specific mortality, and overall survival in our group of patients undergoing NTR / proton-beam radiation therapy (PBRT) and chemotherapy
- To obtain tissue of these rare tumor types for IMPACT assessment. Results of IMPACT testing will be banked for future investigation

### **3.1 BACKGROUND AND RATIONALE**

#### **3.2 Nasal Cavity / Paranasal Sinus Tumors**

Locally advanced malignancies of the nasal cavity and paranasal sinuses that invade the skull base are rare with unclear management paradigms. Beginning in the 1950s, the "gold standard" for treatment of these malignancies, when resectable, has been a combined transfacial and transcranial approach followed by adjuvant radiation. Memorial Sloan Kettering Cancer Center has been a global leader in the management of these patients and coordinated a large retrospective multi-institutional study that set the standard for rates of both oncologic control and treatment related morbidity for patients with resectable disease. This work was first published in 2003. However, when tumors are deemed unresectable by the multidisciplinary consensus, often because of proximity to the carotid artery, brain parenchymal invasion, or involvement of the orbital apex, radiation (with or without chemotherapy) has been the primary treatment pursued. Outcomes for locally advanced paranasal sinus/nasal cavity tumors that receive radiation (with or without chemotherapy) are significantly worse than seen in patients who undergo surgery followed by radiation (+/- chemotherapy).

In the past 15 years, advances in the pathologic understanding of these tumors, chemotherapeutic treatment options, and radiation technology, has led to significant variation of treatment of locally advanced nasal cavity and paranasal sinus cancers. The definition of "resectability" has been altered and tumors that were once considered nonsurgical (such as those with brain invasion) are now deemed resectable in many centers. Furthermore, single institution studies have demonstrated the technical and oncologic feasibility of endoscopic resection for select early and advanced paranasal sinus and skull base tumors, obviating the need for craniotomy and facial incisions, leading to decreased surgery-related treatment morbidity in certain patients.

Unresectable paranasal sinus and nasal cavity tumors treated with photon radiation (3D conformal or IMRT) +/- chemotherapy have poor outcomes, with MSKCC data revealing overall survival of 15% at 5 years, with a 0% local control rate for patients who receive less than 65 gray to the primary site . In studies of salivary gland tumors, including adenoid cystic carcinoma, historic local control rates with radiation +/- chemotherapy have been 0-43%. This is in contrast to recent retrospective data that shows endoscopic or open surgery and proton radiation (+/- chemotherapy) in a variety of pathologies in locally advanced tumors, yields local control at 1 and 3 years of 92.4% and 82.7%. Russo et al recently published 5-year local control rates after resection and proton radiation to be 77% for those patients who have undergone gross total resection (not synonymous with negative margin surgery—gross total resection includes patients with negative margins and microscopically positive margins).

The suboptimal outcomes related to chemoradiation therapy alone coupled with the promise of trimodality therapy using minimally invasive surgery have introduced the idea of cytoreductive surgery for advanced disease prior to chemoradiotherapy. Although these cytoreductive interventions can often help with symptoms related to the tumor size, the oncologic validity of these approaches have yet to be determined. Jansen et al have published the only study of the utility of subtotal resection in paranasal sinus cancers and they found improved local control and overall survival with debulking and conventional photon IMRT. In a retrospective study by Kawashima et al that did not specifically examine cytoreductive surgery, the authors noted that degree of residual tumor burden after skull base surgery correlated with patient outcomes.

In addition to improved local control, cytoreductive surgery may allow for the reduction of radiation doses to normal structures, such as the optic nerves, chiasm, carotid arteries, and temporal lobes. This could reduce the probability of late cognitive, vascular, and visual toxicities. Historically, convention argued against subtotal surgical resection in these patients, as the only option was open surgery with craniotomy and facial incisions; such operations often required free flap reconstruction and led to prolonged hospital stays, with mortality rates of 5% at the most experienced centers, as well as an overall complication rate of 36%, a central nervous system complication rate of 16% (CSF leak, meningitis, pneumocephalus), and a wound complication rate of 20% (infection, dehiscence, flap necrosis). Prolonged recovery in these patients can also potentially lead to delays in adjuvant chemoradiotherapy. However, the use of minimally invasive surgical techniques have shortened hospital stays, as such procedures obviate the need for external incisions with free flap reconstruction and can decrease the risk of CSF leaks and infections. Such reductions in

the duration of hospitalization enable the initiation of adjuvant therapy sooner. Data on the national level have demonstrated that those undergoing endoscopic excision of paranasal sinus tumors start postoperative radiation (+/- chemotherapy) approximately 20 days earlier than those undergoing open craniofacial resection. In addition, on the national level there is no significant difference in the time to starting radiation after diagnosis for those undergoing endoscopic surgery plus radiation compared to those not receiving surgery at all.

The feasibility and oncologic efficacy of near-total resection in unresectable paranasal sinus/nasal cavity tumors followed by PBRT and chemotherapy have yet to be studied in any prospective fashion. This is in contrast to clival chordomas, which occur in the same anatomic region and for which near-total resection coupled with adjuvant chemoradiotherapy has been shown to result in better outcomes than nonsurgical or less aggressive surgical treatment alone. The extent of resection of chordoma has been directly correlated to outcomes in a meta-analysis. In other brain and base of skull lesions, the degree of resection as a continuous variable is positively associated with survival. Proton beam radiation, which is the preferred option for the treatment of skull base and pediatric tumors at many centers, can potentially minimize toxicity to adjacent structures to an even greater degree than was possible previously. The combination of near-total endoscopic resection, because of its reduction in gross disease requiring the highest dose of radiation, and proton radiation, because of its ability to spare normal tissue, may lead to significant reductions in treatment-related toxicity.

The prior studies including Jansen et al are retrospective assessments of outcome based on extent of surgical resection followed by adjuvant treatment, for patients that are presumably resectable. Our study is a prospective evaluation of the utility of addition of surgery in patients that otherwise may not have received it in order to assess the utility of endoscopic near total resection and proton radiation with chemotherapy. We want to rigorously study in a prospective fashion the ability to improve oncologic outcomes for patients with this rare tumor type.

### **3.3 Characteristics of endoscopic skull base resection**

Endoscopic skull base surgery is a widely accepted modality for treatment of both benign and malignant lesions of the nasal cavity and the skull base. The goal, as with any oncologic surgery, is complete resection of the tumor with negative margins. The use of advanced technology has revolutionized surgical management in the paranasal sinuses. Relatively recently adopted use of high definition angled endoscopes enable magnified visualization which can assist in determining normal and abnormal anatomy. This enables the surgical team to ensure resection of all abnormal tissue. In addition, endoscopic resection relies on use of intraoperative image guidance, which similarly helps in ensuring safe resection of tumor surrounding critical structures. Resection can be tailored intraoperatively in real time based on PET, MRI, or CT scan findings. These technologies greatly assist in optimizing the goal of improved local control.

As noted previously, endoscopic excision also provides the potential advantages of obviating craniotomy or facial incisions and a more straightforward reconstruction in the presence of undisturbed tissue planes. Open surgical approaches may provide better access to certain

areas including soft tissues of the cheek, intraorbital contents, and significant intracranial extension, however, an endoscopic resection approach does provide adequate access for many patients without an extensive craniotomy and lateral rhinotomy (facial incision). In addition, the adoption of the regional vascularized nasoseptal flap provides a safe way to reconstruct large intranasal defects, preventing the need for free flap or other reconstruction. Because of the minimally invasive nature of the techniques, patients undergoing endoscopic skull base surgery leave the hospital significantly earlier than those undergoing open surgery and, consequently, the time to adjuvant treatment is decreased. In addition, for locally advanced lesions, a cytoreductive surgery can potentially decrease the tumor volume prior to adjuvant radiation in an anatomic area where a difference of a few millimeters in the radiation target area can be critical.

[figure not shown]
### **3.4 Characteristics of Proton Beam Radiation Therapy (PBRT)**

Intensity modulated radiation therapy (IMRT), the most commonly used form of photon beam radiation therapy in the treatment of HNC, uses multiple x-ray beams to irradiate a tumor target, but deposits not insignificant exit dose delivered to normal tissues beyond the treatment target. PBRT utilizes multiple beams of directed protons to irradiate a tumor target. But in contrast to photons, protons deposit the bulk of their energy at the last few millimeters of their range without any significant exit dose. Both radiotherapy modalities aim to maximize the dose of radiation to the tumor while sparing surrounding normal tissues like the oral cavity, salivary glands, larynx, muscles of the head and neck, spinal cord, and brainstem. However, given the physical characteristics of protons (i.e. minimal exit dose), PBRT may deliver radiation with less accompanying morbidity from damage to surrounding non-malignant tissue when compared with IMRT (Figure 1). This is especially critical in the skull base where damage to adjacent structures such as the brainstem, optic nerves, orbit, brain parenchyma can have catastrophic consequences. Indeed, the need to limit dose to normal structures often results in some degree of underdosing to paranasal sinus and nasal cavity tumors. Because PBRT dramatically reduces the dose of radiation to normal structures, it may allow for a larger proportion of tumor to receive therapeutic radiation doses. Indeed, a recently published retrospective study presented evidence that such a benefit leads to improved local control compared to photon radiotherapy.

However, despite these potential advantages to PBRT, it is uncertain as to whether the reduction in low and intermediate dose exposure to CNS tissue and consequent ability to provide tumoricidal doses to tumor results in a clinically meaningful decrease in toxicities and increase in local control. In addition, PBRT has greater intrinsic uncertainties than standard of care IMRT, such as the exact range of protons in tissue. Although these uncertainties have been mitigated in clinical practice for decades, there remain some unanswered questions, and prospective studies are needed to better characterize the impact of radiation dose alterations on clinical outcomes. [PBRT could result in increased skin toxicity compared to](#)

photon-based therapy.

Figure 1: Representative images comparing IMRT (A) and PBRT (B) treatment plans.

### 3.5 Patient Reported Outcome (PRO)

A patient reported outcome (PRO) is a measurement of a patient's health status that is obtained directly from the patient without interpretation of the patient's responses by a clinician or research associate. The Health and Medicine Division (formerly the Institute of Medicine) of the National Academies of Medicine and the Food and Drug Administration (FDA) have called for measuring PROs as primary or secondary endpoints of clinical trials. Studies have shown that PROs can be more reflective of the patient experience and provide more complementary toxicity and symptom data than clinical or Common Terminology Criteria of Adverse Events (CTCAE) assessments alone. In this trial, the secondary endpoints will be based on clinician-reported CTCAEs as well as patient reported outcomes.

Radiotherapy to the head and neck and, more specifically, to the skull base, is associated with marked acute and late adverse effects. Acute effects include paranasal sinus crusting and bleeding, mucositis, dysphagia, fatigue, dysgeusia, loss of voice, nausea, and fatigue. Late effects include xerostomia, dysphagia, trismus, permanent skin changes, neck fibrosis, and secondary malignancies. Careful assessment of treatment related morbidity is important, as patients who experience significant acute side effects of HNC radiation therapy are reported to have a decreased quality of life. Significant deterioration is associated with those who report having trismus, xerostomia, dysgeusia, and dental problems. PBRT can deliver radiation with reduced dose to nearby normal tissues (e.g., oral cavity, major salivary glands, larynx, cochlea, spinal cord, brainstem, and brain), and potentially improve PRO. However, research on PRO after proton therapy is scarce.

### 3.5 IMPACT Testing

IMPACT testing will be done on all patients under IRB protocol #12-245. All patients will be consented to 12-245 and will have a piece of their specimen along with corresponding bloods taken perioperatively. All biospecimen collection and handling will follow the standard

procedure for 12-245 patients. This testing is important for this study, because of the extremely rare nature of the disease. As there are a small number of rare pathologies assessed in this study, specific questions for IMPACT assessment are challenging a priori. In the future, we will likely couple our IMPACT results with corresponding pathologic specimens.

### **3.6 Summary**

The treatment of locally advanced paranasal sinus and skull base tumors is challenging. Patients deemed to have unresectable disease have significantly worse outcomes with these large-volume tumors, which are typically treated with chemotherapy and radiation; the associated toxicities can be significant. Endoscopic near-total resection, when compared with open surgery, offers the possibility of tumor debulking with minimal morbidity and shorter recovery. We hypothesize that multimodality treatment involving endoscopic near-total resection and adjuvant proton radiotherapy will both minimize toxicity and, most importantly, improve local control. A treatment paradigm involving the potential dosimetric advantages of postoperative proton treatment as well as minimal morbidity for endoscopic resection has the potential to change the treatment approach for patients with these lesions.

The primary endpoint of this study is to assess the local control for patients with unresectable disease, with secondary endpoints of distant metastasis development, disease free survival, overall survival, morbidity of treatment, and patient reported outcomes. Our study may also help to standardize treatment algorithms which, at this time, are widely divergent for patients with unresectable disease. If patients in this study demonstrate favorable outcomes, future studies could address the feasibility of cytoreductive surgical techniques with adjuvant chemotherapy and proton-beam radiation to improve outcomes in patients with “resectable” disease.

## **4.1 OVERVIEW OF STUDY DESIGN/INTERVENTION**

### **4.2 Design**

This is a single center, phase II, single-arm trial assessing the efficacy of local control of near-total endoscopic resection followed by proton-beam radiation with concurrent chemotherapy in unresectable paranasal sinus/nasal cavity tumors. The primary endpoint is local control at 1 year from the end of treatment with failure defined as progression of disease by > 20% of the 12 month post treatment MRI (per RECIST) compared to the post- surgical MRI. If a patient dies during treatment, he/she will be counted as a failure. We will secondarily assess regional/nodal failure and distant metastases, overall survival, disease specific mortality, and progression free survival. Treatment toxicity will be assessed by the Clavien-Dindo Classification of Surgical Complications and CTCAE v4.03 as well as PRO measures including EORTC HN and SBI. IMPACT testing will be performed for all patients undergoing treatment for this rare disease. Results of IMPACT testing will be banked for future investigation. We will include patients with a variety of histologic diagnoses including squamous cell carcinoma (SCC), esthesioneuroblastoma, adenoid cystic carcinoma, and adenocarcinoma. Patients will be included if there is multidisciplinary consensus that the primary lesion is not resectable with negative margin surgery without significant morbidity. This could include lesions that (1) involve the carotid artery, (2) invade brain parenchyma, (3) involve the orbital apex, (4) invade the pterygoid musculature, (5) involve the cavernous

sinus, (6) involve the clivus, and/or (7) involve intraconal space. Patients will only be included if there is multidisciplinary consensus that at least 80% of the tumor bulk can be removed without significant risk of morbidity. There is no cut-off for residual disease. Although expected that we will resect >80% of patient's tumor as discussed pre-operatively, if less than this is resected, patient will still proceed with protocol. Patients will be stratified by the pathologic diagnosis.

As this study is going to include patients for which we will be unable to obtain negative margins (resections will take place for patients where we can anticipate removal of >80% but less than the entirety of the tumor). Our prospective study will be evaluating patients who we cannot obtain a negative margin. The inclusion criteria for our study exclude patients with resectable disease. R1 resections will be unlikely due to patient selection but will still be included if they met the initial inclusion criteria.

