### 10.2 Evaluation during follow up (please see Table 4):

- A focused history and physical exam
- Height and weight
- Dental evaluation
- Karnofsky performance status

- CTCAEv4 toxicity and adverse event assessment
- Study specific PRO instruments:
  - EORTC QLQ C30 & H&N43
  - SBI

Table 4. ASSESSMENTS IN PROTOCOL FOLLOW UP*					
Assessments	Source	From End of Treatment			
		3 months (+/- 2 weeks)	6 months (+/- 4 weeks)	12 months (+/- 4 weeks)	24 months (+/- 4 weeks)
History	EMR	X	X	X	X
Physical	EMR	X	X	X	X
Dental Evaluation	EMR		X	X	X
Karnofsky performance status	EMR	X	X	X	X
Toxicity and adverse events (CTCAEv4)	MD	X	X	X	X
MRI of nasal cavity/para-nasal sinuses AND PET/CT that includes diagnostic quality CT of neck.	EMR	X	x	X	X
EORTC QLQ C30/ H&N43	PSA	X	X	X	X
SBI	PSA	X	X	X	X

\*Additional follow-ups are allowed per standard of care but are not protocol mandated. The patient will not need to fill out these QOL questionnaires at regular cancer follow-up visits after the 24-month follow-up visit.

Abbreviations: MD (medical doctor); PSA (Patient self-administered with or without Research Study Assistant assistance); EMR (Electronic Medical Record)

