## **12.0 CRITERIA FOR THERAPEUTIC RESPONSE/OUTCOME ASSESSMENT**

### **12.1 Local Failure**

The main cancer outcome of interest is local failure defined as recurrence of the primary paranasal sinus or nasal cavity cancer within the primary disease site at one year from end of treatment. Local responses to therapy will be recorded using RECIST 1.1 criteria with the baseline comparator MRI being the postoperative/pre-chemoradiotherapy MRI. Progressive disease (PD) per RECIST 1.1 will be defined as a local failure.

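### Local failure, the primary endpoint, is defined in three unreconciled ways; read literally, the two-scan rule in Section 4.2 scores some regrowth as control and fails when no residual is measurable

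*Combined protocol and SAP*

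**What the plan says.** All section references are to the combined protocol and SAP.

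- **Section 2.1, Primary Objective:** "Local failure will be defined using a modification of RECIST 1.1". The modification is not described there or elsewhere.
- **Section 4.2, Design:** "failure defined as progression of disease by > 20% of the 12 month post treatment MRI (per RECIST) compared to the post- surgical MRI". This names two scans and one threshold.
- **Section 12.1, Local Failure:** the event is "recurrence of the primary paranasal sinus or nasal cavity cancer within the primary disease site at one year from end of treatment", with no percentage attached. The same section adds "Progressive disease (PD) per RECIST 1.1 will be defined as a local failure", with the "baseline comparator MRI being the postoperative/pre-chemoradiotherapy MRI".
- **Section 14.0, Biostatistics:** the treatment is declared worth pursuing if no more than 8 of 25 patients have failed one year after treatment ends. Death, loss to follow-up, withdrawal and removal for toxicity all count as failure. The section does not say which definition of local failure feeds the count.

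Three other places bear on the point. Section 4.2 states "There is no cut-off for residual disease" and, on resections that leave only microscopic disease, "R1 resections will be unlikely due to patient selection but will still be included if they met the initial inclusion criteria". Table 4 in Section 10.2 schedules "MRI of nasal cavity/para-nasal sinuses AND PET/CT that includes diagnostic quality CT of neck" at 3, 6, 12 and 24 months, with a window of 4 weeks either side of month 12. Section 13.1 takes a patient off study if local progression occurs at any time.

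**The concern.** Sections 4.2 and 12.1 share a baseline scan but differ in the event (percentage growth, recurrence, or progressive disease) and in the scans used. Section 4.2 is the most explicit of the three statements, so an analyst might apply it as it stands. It then behaves badly in two foreseeable situations.

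First, patients are selected because tumour is expected to remain, and that residual is then irradiated. It may shrink and later regrow. A rule that compares only the first and last scans does not see the low point between them, although MRIs at 3 and 6 months would show it.

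Second, a percentage change cannot be formed if the post-surgical MRI shows no measurable tumour.

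At stake is the count on which the trial's single decision rests. If the choice between definitions is left until results are known, it could be made with the outcome in view.

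**Working it through.** **1. The plan's own figures.** Inputs from Section 14.0: N = 25, success if at most 8 failures, null failure rate 50%, alternative 25%, stated type 1 error 0.05 and type 2 error 0.15.

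- Null mix: (15 × 0.40 + 10 × 0.65)/25 = 0.50, as stated.
- P(Bin(25, 0.50) ≤ 8) = 0.0539, which rounds to 0.05.
- P(Bin(25, 0.25) ≤ 8) = 0.8506, so type 2 error is 0.149, which rounds to 0.15.

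The stated error rates reproduce to two decimals and are not in dispute here.

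**2. Regrowth after shrinkage.** Let the post-surgical size be 1 and the smallest later size 1 − s. Section 4.2 scores failure only above 1.2. Regrowth from the smallest size that is still scored as control is therefore at most 1.2/(1 − s) − 1.

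| Shrinkage s | Regrowth allowed |
|---|---|
| 10% | 1.2/0.9 − 1 = 33% |
| 20% | 1.2/0.8 − 1 = 50% |
| 30% | 1.2/0.7 − 1 = 71% |
| 50% | 1.2/0.5 − 1 = 140% |

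**3. Illustrative patients** (sizes are assumed; the documents give none).

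| Post-surgical, smallest, 12 months | Section 4.2, literal | Section 12.1 |
|---|---|---|
| 20, 10, 20 mm | (20 − 20)/20 = 0%: control | Doubled from the smallest size; unclear, as the reference for growth is not stated |
| 30, 15, 27 mm | (27 − 30)/30 = −10%: control | +80% from the smallest size; unclear for the same reason |
| 30, 15, 37 mm | (37 − 30)/30 = +23%: failure | Growth exceeds 20% from either reference |
| 0, 0, 12 mm | (12 − 0)/0: undefined | Recurrence at the primary site: failure |

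**4. How close the decision is to one patient.** Adding one failure reverses the conclusion when the count is 8; removing one reverses it when the count is 9.

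- True rate 25%: P(8) + P(9) = 0.124 + 0.078 = 0.20.
- True rate 50%: P(8) + P(9) = 0.032 + 0.061 = 0.09.

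These are the chances of being at the boundary. They are not the chances that a patient is misread.

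**The case against.** The strongest reply is that the literal reading ignores two words. Section 4.2 says its threshold is taken per RECIST, so the sentence may be overview shorthand. Section 12 is the section titled for outcome criteria; its wording is not confined to two scans, and the post-surgical baseline it names may be the modification meant in Section 2.1. This is fair, and it means misclassification is not proven. It does not settle the matter. No section says that 12.1 governs, and none says whether growth is measured from the post-surgical scan or from the smallest later one. RECIST is cited but not reproduced.

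It is also fair that the statement about no residual cut-off mainly concerns large residuals, since the text around it deals with resections falling short of 80%. Only the sentence on microscopic residual supports the unmeasurable case, and the protocol expects that case to be unlikely. The recurrence wording of Section 12.1 covers it.

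A reader might infer three stronger things that the documents do not support:

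- **That progression before month 12 is lost.** Sections 12.1, 13.1 and 14.0 together capture it, though what counts as progression after shrinkage remains open.
- **That Sections 4.2 and 12.1 give opposite verdicts on a given patient.** In the regrowth case 12.1 is ambiguous rather than opposed. In the unmeasurable case 4.2 is silent rather than opposed.
- **That type 1 error is inflated, or power reduced, by a known amount.** Shifting any rule of this kind by one patient changes both, but nothing shows how often that would happen here. The documents also do not say how the historical 50% was scored.

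**Conclusion.** The point stands as an unreconciled definition of the primary endpoint that should be corrected before 12-month MRIs are read. Applied literally, the Section 4.2 rule lets a residual that shrank by 30% or 50% regrow by up to 71% or 140% without counting as failure, and it cannot be computed from a baseline of zero. Both results follow from the arithmetic of that one sentence and need no knowledge of RECIST.

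The practical effect is not quantified. It depends on how many residuals shrink and then regrow within the year, how many patients have no measurable residual, and which section the team actually applies. The documents give none of these. What can be said is that the decision turns on a single patient whenever the count is 8 or 9.

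**What to change.** Make Section 12.1 the single governing definition. Delete the two-scan formula from Section 4.2, and have Sections 2.1, 4.2 and 14.0 refer to 12.1. State in 12.1 that:

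- local failure is either (a) more than 20% growth over the smallest measurement from the post-surgical MRI onward, or (b) new or recurrent tumour within the primary site, whether or not a measurable residual is present;
- it is judged on every scan up to and including the protocol's 12-month MRI, within its window of 4 weeks either side;
- a patient who has failed stays failed.

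Whether to add a minimum absolute increase in millimetres is for the radiology team to decide before 12-month MRIs are read. The question arises because 20% of a 5, 10 or 20 mm remnant is only 1, 2 or 4 mm. Such a minimum could lower the failure count.

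The cost is a protocol amendment. If the team has been applying Section 4.2 literally, this changes how the primary endpoint is measured and is more than a change of wording. The MRIs at 3, 6 and 12 months are already scheduled, and N and the 17-of-25 rule stay as they are. The main downside is that the failure count may rise, which lowers the chance of meeting the rule.
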